2 OBJECTIVES

Aim 1: Randomize IBS-D subjects to receive either treatment with a nonabsorbable antibiotic rifaximin vs. low FODMAP dietary intervention.

- a) 200 IBS-D patients will be carefully phenotyped using validated questionnaires (IBS symptoms, stool form, psychological function, quality of life) and diet analysis.
- b) IBS-D subjects will undergo baseline testing including glucose hydrogen breath tests (GHBT) to define the presence of SIBO. Fecal microbiota will also be characterized by α - and β -diversity and dominant phyla on 16S RNA analyses.
- c) IBS-D subjects will be randomized to receive either rifaximin 550 mg three times daily $\times 14$ days or low FODMAP diet $\times 4$ weeks under direction of study bionutritionist.
- d) The primary outcome will be changes in mean daily pain or bloating by visual analog scale (VAS) after intervention compared with baseline. Responders to intervention will be defined by $\geq 30\%$ reductions in mean daily pain or bloating by VAS compared with baseline. Secondary outcomes will be defined by reduction in IBS Symptom Severity Scale by ≥ 50 compared with baseline.
- e) Other secondary outcomes, including GI symptoms, stool form, psychological function, quality of life, and diet intake, will be compared to determine if subjects present differently.

Aim 2: Determine using longitudinal analyses how SIBO status and fecal microbiota features associate with response to treatment with rifaximin or a low FODMAP dietary intervention.

- a) Fecal microbial analyses will be repeated at 2, 4 and 5 weeks while GHBT will be repeated at the end of the intervention.

- b) The primary aim will be change in fecal microbial diversity after intervention compared with baseline. We hypothesize that low FODMAP diet will result in a 10-15% increase in diversity in fecal microbiota compared with baseline.
- c) Secondary outcomes including response to treatment with rifaximin or low FODMAP diet will be related to the (i) presence of SIBO on initial testing, (ii) persistence of SIBO after intervention, (iii) abnormal α - and β -diversity on initial testing, (iv) changes in α - and β -diversity as well as in dominant microbial phyla at 2, 4 and 5 weeks, and (v) changes in serum cytokine profiles, including TNF- α , IL-1 β , IL-6, IL-8, and IL-10.

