4 ELIGIBILITY CRITERIA

IBS Patients:

200 consecutive adult subjects \geq 18 years of age at screening who meet the following inclusion and exclusion criteria will be eligible for enrollment:

Inclusion criteria:

- Rome IV criteria for IBS-D
- Subjects will be asked to avoid Pepto-Bismol for 2 weeks prior to GHBT.
- Subjects will be instructed to avoid eating or drinking for 8 hours and avoid smoking for 6 hours prior to the test
- Have colonoscopy or sigmoidoscopy with mucosal biopsy within the past 2 years prior to enrollment
- Have an average score of 4 or higher over a 7-day pre-screen taking online symptom surveys assessing abdominal pain and bloating

Exclusion criteria:

- Underlying celiac disease
- Inflammatory bowel disease
- Other organic disease that could explain their symptoms.
- History of GI tract surgery, except for appendectomy
- Narcotics, antibiotics taken within 3 months or probiotics taken within one month prior to enrollment will not be permitted.
- Previously received formal dietary education, including a low FODMAP diet, for treatment of IBS.
- Previously received antibiotics, such as rifaximin, for treatment of IBS or SIBO.
- Women who are pregnant
- Women who are breastfeeding

Additional IBS subjects and Healthy Controls:

50 consecutive adult subjects \geq 18 years (25 IBS-D and 25 healthy controls) who are undergoing colonoscopy for clinical purposes (e.g. colon cancer screening)

For IBS subjects:

Inclusion criteria:

- Rome IV criteria for IBS-D

Exclusion criteria:

- Underlying celiac disease
- Inflammatory bowel disease
- Other organic disease that could explain their symptoms.
- History of GI tract surgery, except for appendectomy
- Narcotics, antibiotics taken within 3 months or probiotics taken within one month prior to enrollment will not be permitted.
- Women who are pregnant
- Women who are breastfeeding

For healthy controls:

Exclusion Criteria:

- History of chronic GI disorder, such as irritable bowel syndrome, inflammatory bowel disease, and small intestinal bacterial overgrowth
- Narcotics, antibiotics taken within 3 months or probiotics taken within one month prior to enrollment will not be permitted
- Women who are pregnant
- Women who are breastfeeding

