5 SUBJECT ENROLLMENT

Most patients with irritable bowel syndrome are seen in gastroenterology or general medicine clinics. IBS-D patients will be recruited from gastroenterology and general medicine clinics at Taubman Center and in the satellite clinics within the University of Michigan Health System. We will also be sending out letters to patients identified from DataDirect as eligible for the study. Eligible IBS-D subjects will be contacted and given material explaining the nature of the study and introduction to a low FODMAP diet. They will be given time to read the materials. If they choose to participate, they will undergo a one week pre-screening an 11-point numerical rating scale (NRS) for abdominal pain and bloating for 7 days. If the subjects qualify through the pre-screen, they will sign the consent document in the presence of the PI and/or Designee. IBS-D subjects will be enrolled on a first come, first served basis. This approach will ensure that IBS-D subjects are representative of the population of patients with IBS in Southeast Michigan.

Emails to providers in the General Medicine and Gastroenterology clinics in the University of Michigan System, public advertisements, telephone calls, and web postings on UMClinicalStudies.org will also be utilized to recruit IBS-D subjects.

IBS subjects who do not meet inclusion/exclusion criteria will not be enrolled in the study. All data collected from IBS-D subjects who are screen failures will be saved for data analysis.

IBS subjects and healthy controls who are undergoing colonoscopy will be approached in the Medical Procedures Unit to determine their interest in participating in the optional sub-study and to determine their eligibility.

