Trial Protocol: In order to minimize unequal allocation between arms, IBS-D subjects will be randomized using block randomization with random permuted sizes of 2 or 4 in a 1:1 ratio into two arms: one group will undergo treatment with rifaximin 550 mg three times daily for 14 days. The second group will be placed on a low FODMAP diet (≤ 9 grams per day as previously described) for 4 weeks (40,64,65). IBS-D subjects undergoing dietary intervention will undergo consultation with a bionutritionist knowledgeable in low FODMAP diets. A diet plan will be implemented and individualized to subjects based on information from their dietary history. Written information regarding allowable vs. non-allowable food items will be provided to IBS-D subjects and bionutritionists will be available during the study for further education. IBS-D subjects randomized to the low FODMAP diet group will meet with the GI nutritionist at the completion of the 2nd week of dietary intervention to answer any potential questions regarding the diet. IBS-D subjects will complete a 24-hour dietary recall each week or every two weeks during the 4-week dietary intervention to ensure compliance.

Symptom Assessment: IBS-D subjects will record stool frequency, BSFS, and symptom scores for abdominal pain and bloating daily on a diary card. IBS-D subjects will complete questionnaires on a weekly basis during study visits to determine changes in symptoms. Responders to intervention arm (both rifaximin and low FODMAP diet) will be defined as $\geq 30\%$ reductions in mean daily pain or bloating compared with baseline. Secondary outcomes, including reduction in IBS Symptom Severity Scale by ≥ 50 compared with baseline at the end of the interventional arm, will also be monitored. These are both considered to reflect clinically meaningful improvements in IBS (55,57). IBS-D subjects will be seen on a weekly or biweekly basis and diary cards will be collected. Adherence to medications or dietary intervention will also be assessed at that time.

Specific Aim 2: Determine using longitudinal analyses how SIBO status and fecal microbiota-derived metrics associate with response to treatment with rifaximin or a low FODMAP dietary intervention.

2A. Research Approach:

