10 STATISTICAL CONSIDERATIONS

Aim 1:

All of the interventional analyses will be analyzed on an intention-to-treat basis. Each IBS-D subject will act as his/her own control for analysis of the effects of either rifaximin or low FODMAP diet intervention. This paired design inherently eliminates a significant amount of bias/confounding and affords increased statistical power. We will power our study to detect a $\geq 30\%$ improvement in mean daily bloating or abdominal pain after intervention compared with baseline. Using available data from a US study on low FODMAP diet in IBS patients (42), we conservatively estimate that we will require 14 IBS-D subjects in each arm to have $>90\%$ power to detect a mean difference of 1.7 in abdominal bloating scores after intervention via paired t-tests with the expected standard deviation (SD) of ± 1.8 . Thus, our expected enrollment of 32 IBS-D subjects in each arm will be more than sufficient for analyzing this aim (see biostatistical analysis for Aim 2), even if the SD is nearly two-fold larger than expected.

Aim 2:

We will examine both inter- and intra-individual variability in microbiota-derived metrics. We plan to use a paired design to eliminate a significant amount of bias/confounding and increase statistical power. We anticipate that there will be some variability in the three samples collected prior to treatment, and various techniques will be employed to average these data so they are incorporated as the baseline. For example, for α diversity (Shannon index) a simple average of the three time points will be sufficient to

establish a baseline α diversity. Similar techniques will be applied to other community structure metrics, to create “deltas” between post-treatment time points and the baseline.

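### Entry sets no stated minimum for either symptom, but a 30% fall in either one makes a responder, so a low-baseline symptom can produce a response on a small change

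*Combined protocol and SAP*

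**What the plan says.** All references are to the combined protocol and SAP.

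- **Entry (section 4, inclusion criteria):** "Have an average score of 4 or higher over a 7-day pre-screen taking online symptom surveys assessing abdominal pain and bloating". Section 5 identifies the instrument as "an 11-point numerical rating scale (NRS) for abdominal pain and bloating for 7 days" and adds no further severity rule: "If the subjects qualify through the pre-screen, they will sign the consent document". Neither section says how the pain and bloating scores are combined, and neither sets a minimum for each.
- **Response (section 2, Aim 1(d); section 6, 1A and 1B):** a fall of at least 30%. Section 2 words it as "reductions in mean daily pain or bloating by VAS compared with baseline". Section 6, Symptom Assessment, words it as "reductions in mean daily pain or bloating compared with baseline" and applies it to both arms. None of the three places gives a baseline floor for the symptom scored, a minimum absolute change, a rule for a zero baseline, or a condition on the other symptom.
- **Justification (section 6, Symptom Assessment):** of this rule and the IBS Symptom Severity Scale rule (a fall of at least 50), the plan says "These are both considered to reflect clinically meaningful improvements in IBS".
- **Sample size (section 10, Aim 1):** it rests on continuous change, giving "power to detect a mean difference of 1.7 in abdominal bloating scores after intervention via paired t-tests" "with the expected standard deviation (SD) of" 1.8, with 14 per arm.

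**The concern.** The entry rule looks at the two symptoms together, while the responder rule looks at each alone, as a percentage of its own starting value. Nothing links the two. A patient can qualify mainly on one symptom and then be classified on the other, where the denominator is small and ordinary week-to-week variation easily exceeds 30%. The symptom that brought the patient into the trial may not have changed at all.

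Responder status is used beyond Aim 1. Aim 2 relates it to SIBO, diversity and cytokines, and section 10 bases a power statement on comparing responders with non-responders. Aim 3 models response to the diet. If responder labels partly reflect an uneven baseline profile, the Aim 2 associations are weakened. So is the Aim 3 model, if it uses this rule as its label. Choosing pain or bloating as the single responder symptom would not by itself cure the fault, because entry does not ensure that the chosen symptom is present to a useful degree.

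**Working it through.** **1. The plan's own figure.** Paired t-test, mean change 1.7, SD 1.8 (section 10); two-sided alpha 0.05 is assumed because none is stated. The noncentrality is √n × 1.7/1.8. For n = 14 it is 3.53 and power is 90.4%; for n = 13 power is 87.8%. The stated 14 is reproduced. It depends on continuous change and not on the responder rule.

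**2. Size of a 30% fall.** Required fall = 0.30 × baseline.

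| Symptom baseline | Fall needed | Diary points over 7 days |
|---|---|---|
| 0 | undefined | – |
| 0.5 | 0.15 | 1.05 |
| 1 | 0.3 | 2.1 |
| 2 | 0.6 | 4.2 |
| 4 | 1.2 | 8.4 |
| 5.67 | 1.7 | 11.9 |

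The planning effect of 1.7 equals a 30% fall only at baseline 1.7/0.30 = 5.67.

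**3. Worked patients** (pooled average, seven-day windows; the plan does not state the length of the post-treatment window).

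- Pain 7, bloating 1: average (7 + 1)/2 = 4.0, so the patient enters. A bloating mean of 0.7 is a response with pain still at 7. In whole diary points, a bloating total of 7 must lose three points: losing two gives 5/7, a fall of 28.6%, which does not qualify.
- Pain total 3 (mean 0.43), bloating total 53 (mean 7.57): (3 + 53)/14 = 4.00, so the patient enters. If pain falls to a total of 2, one point on one day, the fall is 1/3 = 33% and the patient is a responder. Bloating is unchanged and the combined total falls 1/56 = 1.8%.

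**4. Chance response by level.** Simulation with no true change, weekly means limited to 0-10, week-to-week SD 0.8 (assumed). The chance of a 30% fall in one symptom is 37% at a true level of 1, 27% at 2, 18% at 3, 11% at 4 and 3% at 6. A zero baseline counts as non-response; leaving such draws out would make the first figure 42%.

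**5. Effect in an entering population.** Assumed: pain and bloating each with true mean 4.5 and SD 1.8, correlation 0.3 to 0.7, entry if (pain + bloating)/2 ≥ 4, no true change. None of these values is in the documents.

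| Week-to-week SD | False response, entrants with one symptom below 4: as written / floor of 4 | False response, all entrants: as written / floor of 4 |
|---|---|---|
| 0.5 | 5-7% / 1-2% | 3-4% / 2% |
| 0.8 | about 19% / 9-12% | 14-16% / 12% |
| 1.0 | about 28% / 15-20% | 23-25% / 21% |

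At SD 0.8, 26-36% of entrants have one symptom below 4. Only 0.3-2% have one below 2, and about 0.2% or fewer have one at 1 or below.

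**6. Check with rounded daily scores.** Independent daily scores, day-to-day SD 1.0 to 2.0 (assumed), no true change, entry on the pooled average. With underlying pain 2 and bloating 7, 10-25% are called responders; with both at 5.5, 0.1-7.5% are. The direction is the same.

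**The case against.** **The entry rule is ambiguous and not plainly faulty.** If the sponsor meant an average of 4 on each symptom, the gap closes. This stands as a reason to clarify section 4. But no section states that reading, one average is the plainest reading, and the other alternative (either symptom at 4 is enough) leaves the gap open.

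**The extreme patients are rare and the overall effect is small.** This stands. A reader might infer from the worked patients that many entrants have almost none of one symptom. The documents give no distribution of baseline scores, and in the model above such patients are well under 1%; most of the excess comes from baselines between 2 and 4. At SD 0.8, patients with both symptoms at 4 or more already show 12-14% false response, so most false response comes from the either-symptom rule and the assumed variability, and a floor would not remove it.

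**The main analysis does not depend on this rule.** This also stands. A reader might infer that the primary outcome or the 14 per arm is undermined, but both rest on continuous change. The Symptom Severity Scale criterion is an absolute fall and is free of this denominator problem. It is a separate outcome, however, and does not correct the 30% rule. The plan does not say that the Aim 3 label is the 30% rule, so harm to that model is conditional.

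**Restricting the bloating change score to patients with baseline bloating of at least 4** is a tempting extension that should not be adopted. In the same model with no true change (SD 0.8), it raises the spurious before-after fall from about 0.12 to 0.20-0.22 points through regression to the mean. It also drops 13-18% of patients and sits badly with the intention-to-treat statement in section 10.

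**Conclusion.** The point holds as a fault in the responder definition. On the plain reading of section 4, the rule in sections 2 and 6 can classify a patient as a responder on a change too small for the clinical meaning that the plan gives it, and it has no answer at a zero baseline. That conclusion needs only arithmetic.

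The size rests on assumed means, SDs and correlation. On those assumptions, a floor of 4 roughly halves false response among entrants with one low symptom when the week-to-week SD is 0.8. Across all entrants it lowers false response by about 2 to 4 percentage points. The size in this trial is unknown. The effect falls on the responder analysis, on the Aim 2 response associations, and on Aim 3 if it uses this label. It should be corrected because correction is cheap and the label is reused, but it does not threaten the main comparison of change scores. The naming of a VAS in the definition, where an 11-point numerical scale is collected, is a separate matter.

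**What to change.** - **Section 2, Aim 1(d), and section 6 (1A and Symptom Assessment):** add that a 30% response is scored only on a symptom whose own baseline mean is at least 4, the plan's entry figure, so that a lower-baseline symptom cannot make a patient a responder. This also settles the zero-baseline case.
- **Which week sets the floor:** if the pre-screen week and the baseline differ, apply the floor to the pre-screen week. The larger of two scores is never below their average, so every patient admitted on a pooled average of 4 or more then has at least one scorable symptom.
- **Section 4:** state how the pain and bloating scores form the entry average.
- **Continuous change analysis:** keep all randomised patients in it.

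The cost is about one sentence in each place. Pain and bloating are already recorded separately, so no new data or visits are needed and the sample size is unchanged. The downside is a slightly lower responder rate.

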3 EXPECTED RISKS/BENEFITS

The data accumulated in this study will advance our understanding of the pathophysiology of IBS, including the role of the gut microbiota and SIBO in the pathogenesis of IBS, and may provide important information on which IBS subjects will most benefit from therapies including dietary modification and rifaximin.

There are potential direct benefits for all IBS subjects in this study. On study entry, glucose hydrogen breath tests (GHBT) as well as analysis of fecal microbiota will be performed that may provide new insight into causes of symptoms in patients with IBS. Furthermore, subjects with IBS will be treated with well accepted treatments for IBS, including a nonabsorbable antibiotic rifaximin or diets low in FODMAP. IBS-D subjects treated with low FODMAP diet will be provided education on a low FODMAP diet from a trained bionutritionist. IBS-D subjects will track their symptoms by completing questionnaires online including the Bristol Stool Form Scale as well as an 11-point NRS on abdominal pain and bloating daily. IBS-D subjects will be asked to complete these questionnaires after their evening meal. They will also be instructed to track their diet for 24 hours prior to each weekly or biweekly visit using a food questionnaire. Finally, all IBS-D subjects will be seen or receive a phone call by the PI and/or study team every week or every two weeks during the study. At each visit, survey information will be obtained using validated questionnaires including IBS-Symptom Severity Scale, Gastrointestinal Symptom Rating Scale-IBS, Patient Health Questionnaire (PHQ-9), Visceral Sensitivity Index (VSI), and IBS-quality of life (IBS-QOL). The IBS-Symptom Severity Scale is a 10-item questionnaire that tracks severity of IBS symptoms and is a

valid way to monitor changes in IBS symptoms over time. This will take approximately 5 minutes to complete. The Gastrointestinal Symptom Rating Scale-IBS is a 15-item questionnaire that tracks both upper and lower gastrointestinal symptoms. This will take approximately 8 minutes to complete. The PHQ-9 is a 9-item questionnaire that is a reliable and valid measure of depression severity. This will take approximately 5 minutes to complete. The VSI is a 15-item questionnaire which is a reliable, valid measure of GI-specific anxiety. This will take approximately 8 minutes to complete. The IBS-QOL is a 34-item questionnaire that is a reliable, valid quality of life measure specific for IBS. This will take approximately 15 minutes to complete. This frequent and comprehensive assessment provided as part of participating in this study may allow for closer monitoring of disease course.

There are potential risks for subjects, including:

- 1) Risk to privacy (rare): There is a potential risk to the IBS-D subject's privacy (<1% risk). While every effort will be made to maintain privacy, it is possible that others may learn about information acquired from the medical records.

For Aim 3, there are additional risks to privacy associated with secondary review of data from a separate database (HUM 00053274). However, we will follow standard procedures to minimize these risks. This includes use of data abstraction forms that will not contain any PHI. All subjects will be identified by a study ID number. The list linking the subject to his/her study ID number will be retained by the investigators in a secure location separate from the source documents. The list linking PHI to study ID numbers will be accessed only for verification of data abstraction if any inconsistency or incompleteness of study data requires review of a participant's medical record. Once the data has been reviewed, analyzed, and verified, and the investigators are satisfied that no further review of the subject's medical record is needed, the list of links to the identifiers for that subject population will be destroyed. This will ensure that no links to PHI persist beyond the duration of the study. No PHI will be sent outside of the institution. All presentations/publications will deal with data in aggregate form. Source documents created for study purposes will identify patients by study ID number only and will not contain PHI.

- 2) Glucose hydrogen breath testing (likely): IBS-D subjects will be asked to drink 75 g of glucose dissolved in 250 ml of sterile water. IBS-D subjects may experience (10-25%) bloating, abdominal cramping, and/or flatulence after consuming this drink. However, symptoms typically resolve quickly and may represent underlying physiologic abnormalities causing their symptoms. Subjects will be allowed to take medications, such as simethicone or Tylenol, if they experience significant bloating or discomfort. IBS-D subjects may experience dizziness, faint spells, and/or nausea after the glucose hydrogen breath test. Subjects should bring a snack with them on

days that the hydrogen breath test should be done to help with dizziness and lightheadedness.

- 3) Risks of Blood Draw: If subjects decide to participate in optional sub-study, 10mL of blood will be drawn from a vein at Visits 1 and 5. There could be pain, bruising, or lightheadedness. Rarely there could be an infection or fainting. The person drawing blood will be trained to do that procedure and use techniques to minimize these risks.
- 4) Risks of treatment (infrequent): There are theoretical concerns about treatment with rifaximin and low FODMAP diet. Rifaximin is an antibiotic and theoretical concerns exist regarding potential for antibiotic resistance. However, rifaximin is a minimally absorbable antibiotic with low risk of clinically relevant bacterial resistance (50,51). Randomized controlled trials with rifaximin in IBS have not demonstrated significant differences in adverse events between rifaximin and placebo (31,32,52). General antibiotics side effects may occur, such as vomiting, nausea, diarrhea, etc. There are also theoretical concerns that prolonged therapy with a low FODMAP diet may have detrimental effects on gut microbial composition (53). However, multiple studies examining low FODMAP diet in IBS have demonstrated the safety and tolerability of this dietary approach (40–42,45). The effects of rifaximin in pregnancy and women who are breastfeeding are unknown and therefore pregnant women or women who are breastfeeding will be excluded from the study. Finally, women of child bearing age will be warned that oral contraception may not be as effective when taken with rifaximin.
- 5) General risks (infrequent): This is an interventional study. IBS-D subjects' condition may worsen or improve while undergoing intervention with either rifaximin or a low FODMAP diet. Participation in this study will not prevent normal clinical care of IBS or its consequences. In addition, some prescribed medications may need to be stopped temporarily during the study. This includes medications that may influence pain sensation, including narcotic pain medications. IBS-D subjects will also be asked to discontinue antibiotics for at least 3 months and probiotics for at least 1 month prior to enrollment. IBS-D subjects will be asked to avoid Pepto-Bismol for at least 2 weeks prior to GHBT. IBS-D subjects will also be instructed to eat a low carbohydrate diet for at least 2 days prior to the GHBT to avoid inaccurate test results. If IBS-D subjects are taking any of these medications, their symptoms may return or worsen when they are stopped. However, the stopping of medications is temporary and is not felt to cause any undue hardship. Finally, there is a risk that some of the questions in the surveys may produce emotional distress. If the IBS-D subject desires, he/she can be referred to

a mental health specialist within the UMHS or another provider outside the UMHS system.

6) Risks for sharing samples (rare): If subjects decide to participate in an optional sub-study, saliva samples will be shared with Karolinska Institute and IKMB Kiel to evaluate differences in sucrase-isomaltase SNPs. There are potential risks to the IBS-D subject's privacy. However, all samples will be de-identified and only investigators at UMHS will have access to the linkage code.

